The recommended phase II dose (RP2D) will generally be the MTD, but it may be less than the MTD based on a review of available data/cumulative toxicities and activity.

Phase II Design:

The phase II portion of this study will implement a Gehan two-stage design to estimate the response rate and to evaluate the activity of 8-chloro-adenosine when given as a single agent (Gehan, 1961). The phase II portion of the study is expected to enroll a minimum of 9 and a maximum of 25 patients. Patients treated at the RP2D in the phase I portion of the study, who receive at least 2 cycles of treatment, will count toward the 25 patients required. The sample size is based on the desire to estimate the response rate with at most 10% standard error, and early stopping if the treatment is unexpectedly ineffective.

At stage 1, 9 patients will be entered on the study. If 0 responses are seen in the first 9 patients treated, the study will be terminated and the true regimen response will be declared $\leq 30\%$. If at least 1 patient responds, the trial will continue to the second stage. Because patients treated during the phase I portion of the trial at the dose selected for the phase II trial will be counted ($n=6$), only 3 additional patients will be enrolled at stage 1. Under this design if the study agent is $>30\%$ effective, there would be 96% chance of at least one success.

At stage 2, 16 additional patients will be entered. This accrual provides for estimation of the response rate with no more than 10% standard error.

Endpoints:

Phase I:

The primary endpoint is toxicity. Toxicity will be graded according to the NCI-Common Terminology Criteria for Adverse Events version 4.03. Dose limiting toxicity (DLT) and moderate toxicity are defined in section 13.2 of the protocol. Note: The phase II portion of the study will use the DLT definition to define unacceptable toxicity. The MTD will be based on the assessment of DLT during cycle 1. All patients who are not evaluable for dose limiting toxicity will be replaced.

Phase II:

The primary endpoint is complete remission rate (CR/CRi) and is based on the Döhner et al. 2010 criteria²⁴. Response will be assessed at the end of each cycle/just prior to the start of each cycle. Secondary endpoints include: remission duration, survival (overall and event-free) and toxicity.

Clinical Pharmacology Endpoints:

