6.1.2 Possible anticipated toxicities to 8-chloro-adenosine

Events seen in chronic lymphocytic leukemia patients regardless of attribution that were at least two grades over baseline are listed with the highest grade indicated:

Hematologic: anemia (G3), neutropenia (G4), thrombocytopenia (G3)

Gastrointestinal: abdominal pain (G3), diarrhea (G2),

Metabolic: hypercalcemia (G4), hyperglycemia (G3), hypouricemia (G2),

General/Other: back pain (G3), fever (G2), sunburn (G2), flu syndrome (G2)

Toxicities seen in animal studies (murine and canine) using a range of regimens and doses (Section 2.5) are as follows:

Hematologic: transient thrombocytopenia

Gastrointestinal: vomiting

Renal: elevated BUN, renal nephrosis

General/Other: decreased activity, sloughing of the skin, dyspnea

Toxicities which may be foreseeable based on toxicities seen with other adenosine analogues (Cladribine, Didanosine, Fludarabine, Tenofovir) include the following (note: the asterisk indicates extremely rare but serious events):

Hematologic: thrombocytopenia, neutropenia, anemia, myelosuppression, pancytopenia*

Dermatologic: pruritus, rash, Stevens-Johnson syndrome*, toxic epidermal necrolysis*

Gastrointestinal: vomiting, nausea, diarrhea, abdominal pain, mucositis, stomatitis, anorexia, increased serum amylase, pancreatitis

Hepatic: increased liver enzymes, liver failure*

Metabolic: hyperuricemia

Musculoskeletal: arthralgia, myalgia, bone pain, backache, muscle weakness

Neurologic: headache, peripheral neuropathy, dizziness, insomnia

Renal: increased serum creatinine, renal failure*

Other: anaphylactoid reaction*, alopecia, fatigue, fever, chills, infection, pain, dyspnea, edema, diaphoresis, phlebitis

6.2 Start of Cycle Criteria:

Hematologic toxicities:

- For participants with CR, all hematologic toxicities must resolve to ≤ Grade 2
- For participants without CR, hematologic toxicity maybe of any grade.

Non-hematologic toxicities:

- Non-hematologic toxicities related to study agent must resolve to ≤ Grade 2.
- Non-hematologic toxicities not considered related to study agent may delay of start of cycle criteria per the discretion of the treating investigator.

For holds due to toxicities related to study agent, if the participant does not meet criteria to resume treatment by Day 49 from start of cycle, the participant must permanently discontinue study treatment. See Section 6.3 for dose modifications due to toxicity.

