6.3 Dose Modifications of 8-Chloro-adenosine

6.3.1 General Information

- a. The study will use the NCI Common Terminology Criteria for Adverse Events (CTCAE) version 4.03 to grade toxicities. A copy of the version 4.0 can be downloaded from:
<http://evs.nci.nih.gov/ftp1/CTCAE/About.html>
- b. Intra-patient dose escalation is never permitted in this study. Rules for dose modification for are found in Table 6.3.2.
- c. **For treatment holds if the participant does not meet criteria to resume treatment by Day 49 from start of cycle, the participant must permanently discontinue study treatment.**
- d. When dose reductions are applicable, the dose will resume at the next lowest safe dose. Dose levels including intermediate dose levels for dose reduction are detailed in Table 5.3.1.

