6.3.2 Dose Modifications and Treatment Interruptions

The table below details the specific dose modifications and treatment interruptions for administration of 8-chloro-adenosine; they are to be used in agreement with the information in Section 6.3.1. Unless listed in Table 6.3.2, treatment will continue without interruption or dose modification. Start of cycle criteria will apply to initiate a new cycle of therapy (Section 6.2).

Table 6.3.2 Dose Modifications and Interruptions to 8-Chloro-adenosine Administration*

Adverse Event	Treatment Modification
Non-Hematologic toxicities considered RELATED to 8-chloro-adenosine in all participants:	
Grade 3 toxicity except for the following: 
 • vomiting, nausea, diarrhea that responds to maximum medical therapy • electrolyte imbalance, fatigue, anorexia, asthenia, stomatitis, mucositis, infection, dermatitis 	Hold study treatment until resolution to \leq Grade 2. Resume at pre-hold dose.
Grade 4 toxicity:	Hold study treatment until resolution to \leq Grade 2. Resume at 1 dose level reduction unless the toxicity is a grade 4 electrolyte imbalance correctable within 48 hours or grade 4 vomiting that responds to maximum medical therapy within 48 hours. In such cases patients can resume treatment at the assigned dose without reduction at the Physician's discretion.
Hematologic toxicity RELATED to 8-chloro Adenosine	
Grade \geq 3 peripheral blood cytopenia not resolving to \leq Grade 2 by day 49 from start of cycle in patients who have less than 5% bone marrow blasts	No additional cycles of study drug will be administered
Other unspecified Non-Hematologic Toxicities considered UNRELATED to study agent	
Other unspecified events of any grade considered unlikely or not related to study agent.	Maintain treatment with study agent. Interruption of study treatment is permitted if the investigator consults with the Principal Investigator to determine that this is in the best interest of the participant.

*: See section 5.2 for additional criteria to resume, make up missed doses.

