12.2 Response

The primary endpoint is complete remission rate (CR + CRi) and is based on the Döhner, 2010 criteria²⁴; calculated as the percent of evaluable patients that have confirmed CR or CRi.

Response criteria will be as follows:

CR: Bone marrow with < 5% blasts by morphology. ANC > 10³/µL, platelets ≥ 10⁵/µL

CRi: Bone marrow with < 5% blasts by morphology, not meeting blood count criteria for CR.

PR: Decrease of at 50% in bone marrow blasts

PD: Bone marrow blasts more than 20% and increase in blasts by over 50%.

HR: improvement in hematologic parameters, but not meeting criteria for PR.

Secondary activity endpoints for this study are as follows:

- Duration of response, defined as the time interval from the date of first documented response (CR+CRi) to documented disease relapse or death whichever occurs first.
- Overall survival, defined as the time interval from date of first dose of study drug to date of death from any cause.
- Event-free survival, defined as the time interval from date of first dose of study drug to first documented disease progression or death from any cause, whichever occurs first.
- Overall response rate (CR/CRI/PR), calculated as the percent of evaluable patients that have confirmed CR or CRi or PR.

12.3 Clinical Pharmacology Endpoints:

- For plasma PK, levels of 8-chloro-adenosine, its deaminated metabolite, 8-chloro-inosine, and its base 8-chloro-adenine will be quantitated in plasma during 5 days of therapy.
- For cellular PK, concentrations of 8-chloro-adenosine and 8-chloro-ATP will be quantitated in circulating leukemia cells in the peripheral blood.
- For urine PK, levels of 8-chloro-adenosine, its deaminated metabolite, 8-chloro-inosine, and its base 8-chloro-adenine will be quantitated in urine during the first 24 hours of therapy.
- For PD, the impact of therapy on endogenous ATP pools, as well as the effect on short-lived mRNA transcripts and proteins will be analyzed in circulating acute leukemia blasts.

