Phase II (Evaluable for Toxicity): Patients will be considered evaluable for toxicity if they receive any study drug. Patients enrolled/treated as part of the phase II study will not be replaced based on toxicity.

Phase I and II (Evaluable for Response): For the phase II portion, as part of the primary analysis, patients will be considered evaluable for response if they are eligible, have baseline disease assessments, and receive 2 cycles of protocol treatment or achieve a CR/CRI after 1 cycle of protocol treatment. Patients will have their response classified according to the Dohner 2010 criteria²⁴.

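### Sections 6.2 and 6.3.1c give the Day 49 discontinuation rule different scopes, so it is unsettled whether a patient held past Day 49 for a clearly unrelated event may start the next cycle and become response-evaluable.

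*Combined protocol and SAP*

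**What the plan says.** Section 6.2 (Start of Cycle Criteria) treats unrelated and related toxicity differently. On unrelated toxicity it says: "Non-hematologic toxicities not considered related to study agent may delay of start of cycle criteria per the discretion of the treating investigator". No time limit is attached. The Day 49 rule follows: "For holds due to toxicities related to study agent, if the participant does not meet criteria to resume treatment by Day 49", counted from the start of the cycle, the participant must stop study treatment permanently.

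Section 6.3.1, item c, printed in bold, gives the same consequence and the same clock without the attribution limit: "For treatment holds if the participant does not meet criteria to resume treatment by Day 49 from start of cycle".

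Table 6.3.2 has a row for unrelated events. Its default is to continue treatment, but "Interruption of study treatment is permitted if the investigator consults with the Principal Investigator" and they agree that it serves the participant. That row has no time limit either. The text introducing the table says of its modifications that "they are to be used in agreement with the information in Section 6.3.1", and then adds that the start-of-cycle criteria of 6.2 apply to each new cycle.

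Section 13.1, and the matching synopsis paragraph, make a patient evaluable for response if eligible, assessed at baseline, and able to "receive 2 cycles of protocol treatment or achieve a CR/CRI after 1 cycle of protocol treatment". Section 12.2 defines the primary rate as "calculated as the percent of evaluable patients that have confirmed CR or CRi"; section 13.7 and the synopsis also use evaluable patients as the denominator.

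**The concern.** Take a patient whose cycle 2 is delayed by an event judged clearly unrelated to the drug, and who recovers after Day 49. Under 6.3.1c that patient must stop. Under 6.2 nothing requires the patient to stop, and the delay is a matter of discretion. Two sites of instruction in one protocol therefore lead to different treatment of the same patient.

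The difference carries into the primary analysis. If the patient was not in CR/CRi after cycle 1, stopping means one cycle received, not evaluable, and removal from the denominator. Receiving cycle 2 means evaluable, with a second chance to respond. The synopsis (Phase II Design) adds that patients treated at the RP2D in phase I, "who receive at least 2 cycles of treatment, will count toward the 25 patients required", so the same ambiguity can affect which phase I patients carry over.

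**Working it through.** **1. Do the two rules reach the same patient?** One might assign 6.2 to delays at the start of a cycle and 6.3.1c to holds within a cycle. The text does not make that division, and section 5.2 works against it. Missed doses may be made up only if treatment can resume within 48 hours or by Day 5, whichever is later. After that, treatment resumes with the next cycle if the start-of-cycle criteria are met. A hold still open at Day 49 is therefore always a question about starting a new cycle, to which 6.2 applies. Day 49 is 49 − 28 = 21 days beyond a 28-day cycle under either section.

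**2. Does another section settle the scope?**
- Section 6.3.2 ties Table 6.3.2, including its unrelated row, to 6.3.1 and so to item c. It also sends new cycles to 6.2. It points both ways.
- Section 10 extends the previous cycle until treatment is ready to resume and sets no limit.
- If 6.3.1c is the general rule and 6.2 one instance of it, the restriction to related toxicity in 6.2 has no function, although it comes soon after the bullet on unrelated delays.
- For an unrelated event, the criteria to resume that 6.3.1c relies on are left to the investigator, so how item c would operate is itself unclear.

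**3. The plan's own figures (section 13.1).** These reproduce and are not in dispute.
- Chance of at least one response in 9 at a true rate of 30%: 1 − 0.7^9 = 0.9596, stated as 96%.
- Largest standard error at n = 25: √(0.5 × 0.5 / 25) = 0.100, stated as no more than 10%.

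**4. Size of the effect on the primary rate.** Assumptions: m of 25 patients are held past Day 49 for an unrelated event without CR/CRi after cycle 1; they are not replaced; there are 5 responders among the others. The documents give no value for m, so 1 to 3 is shown.

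| m | 6.3.1c governs: 5/(25 − m) | 6.2 governs, none of the m responds | 6.2 governs, all m respond: (5 + m)/25 | Largest SE at n = 25 − m |
|---|---|---|---|---|
| 1 | 5/24 = 20.8% | 5/25 = 20.0% | 6/25 = 24.0% | 10.2% |
| 2 | 5/23 = 21.7% | 5/25 = 20.0% | 7/25 = 28.0% | 10.4% |
| 3 | 5/22 = 22.7% | 5/25 = 20.0% | 8/25 = 32.0% | 10.7% |

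The last two rate columns are bounds. For m = 1 the exact 95% intervals are 6.8% to 40.7% for 5/25 and 7.1% to 42.2% for 5/24, which are almost the same. The largest SE occurs at a true rate of 50%. At 30% it is √(0.21/25) = 9.2% for n = 25 and √(0.21/22) = 9.8% for n = 22, both under 10%.

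**5. Where the exclusion comes from.** Patients who stop after one cycle without CR/CRi leave the denominator because of the evaluability definition, whatever their reason for stopping. The Day 49 scope only decides whether some patients fall into that group.

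**The case against.** The strongest reply is that there is no flat contradiction. Section 6.2 never says that an unrelated hold may run past Day 49; it is silent. A site applying 6.3.1c to every hold would breach no sentence of 6.2, and the cross-reference in 6.3.2 gives some support for doing so. This stands as far as it goes: the conflict lies between a limited rule plus an open-ended discretion and an unlimited rule. It does not remove the ambiguity, because 6.3.2 also sends new cycles to 6.2.

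The reply is also right that few patients can be affected. Events count as related unless clearly unrelated (sections 7.2 and 13.2), and Table 6.3.2 continues treatment by default for unrelated events. The patient must also be held past Day 49, be without CR/CRi or progression, and then recover. Section 5.7 separately allows treatment to end for intercurrent illness or a change in condition, so many such patients could stop under either reading.

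Section 11.2.3 has the investigational drug service rely on the principal investigator when the protocol is ambiguous. That gives an answer case by case, and by then the end-of-cycle-1 response will usually be known. The study calendar says that this response does not determine whether cycle 2 is given, which is a partial safeguard, but it does not supply a scope for the Day 49 rule.

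A reader might infer that the choice of scope could move the result across the 30% reference rate. Removing three non-responders does this only with exactly 7 responders (7/25 = 28.0%, 7/22 = 31.8%): with 6, 6/22 = 27.3% stays below, and with 8, 8/25 = 32.0% is already above. More importantly, the final analysis is an estimate with an exact interval and has no test against 30%. A reader might also infer that the 96% stage 1 figure is eroded. The stage 1 rule is stated for the first 9 patients treated, not the first 9 evaluable, so the documents do not support that.

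**Conclusion.** The point holds as an inconsistency that needs reconciling. Sections 6.2 and 6.3.1c give the same mandatory rule different scopes, and nothing else in the protocol says which governs a clearly unrelated hold that resolves after Day 49. The consequence for the individual patient is whether another cycle may be given. The consequence for the analysis is whether a patient without CR/CRi after cycle 1 is counted; a patient already in CR/CRi is evaluable either way.

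The numerical effect is modest. One affected patient moves the illustrated rate by 0.8 percentage points through the denominator alone, or by 3.2 points (24.0% against 20.8%) if that patient would have responded in cycle 2. This rests on an assumed number of affected patients and an assumed five responders among the others. No planned decision is shown to change. Confidence is high in the textual difference and much lower in any material effect on the reported rate.

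**What to change.** Reconcile section 6.2, section 6.3.1 item c and Table 6.3.2 so that a single Day 49 rule states whether it covers holds for related toxicity only or all holds, and word it the same way in each place. Which scope applies is for the sponsor's clinicians. This is a wording change and adds no visits or patients.

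Separately, amend the evaluability and primary-rate definitions (sections 12.2, 13.1 and 13.7, and the matching synopsis paragraphs). Every eligible treated patient with a baseline assessment who stops before cycle 2 without CR/CRi, for any reason including the Day 49 rule, should count as a non-responder in the primary rate. Limiting this to Day 49 stops would close one route of exclusion and leave the others open. The two-cycle condition on phase I patients in the synopsis should be checked against the new definition.

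The cost is a change to the primary analysis set and a slightly lower reported rate: in the one-patient illustration, 5/25 = 20.0% in place of 5/24 = 20.8%. It does not make the rate independent of the scope chosen, since a patient allowed cycle 2 could still respond (6/25 = 24.0%). It does keep such patients in the denominator under either scope.

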6.3 Dose Modifications of 8-Chloro-adenosine

6.3.1 General Information

- a. The study will use the NCI Common Terminology Criteria for Adverse Events (CTCAE) version 4.03 to grade toxicities. A copy of the version 4.0 can be downloaded from:
<http://evs.nci.nih.gov/ftp1/CTCAE/About.html>
- b. Intra-patient dose escalation is never permitted in this study. Rules for dose modification for are found in Table 6.3.2.
- c. **For treatment holds if the participant does not meet criteria to resume treatment by Day 49 from start of cycle, the participant must permanently discontinue study treatment.**
- d. When dose reductions are applicable, the dose will resume at the next lowest safe dose. Dose levels including intermediate dose levels for dose reduction are detailed in Table 5.3.1.

6.3.2 Dose Modifications and Treatment Interruptions

The table below details the specific dose modifications and treatment interruptions for administration of 8-chloro-adenosine; they are to be used in agreement with the information in Section 6.3.1. Unless listed in Table 6.3.2, treatment will continue without interruption or dose modification. Start of cycle criteria will apply to initiate a new cycle of therapy (Section 6.2).

Table 6.3.2 Dose Modifications and Interruptions to 8-Chloro-adenosine Administration*

Adverse Event	Treatment Modification
Non-Hematologic toxicities considered RELATED to 8-chloro-adenosine in all participants:	
Grade 3 toxicity except for the following: 
 • vomiting, nausea, diarrhea that responds to maximum medical therapy • electrolyte imbalance, fatigue, anorexia, asthenia, stomatitis, mucositis, infection, dermatitis 	Hold study treatment until resolution to \leq Grade 2. Resume at pre-hold dose.
Grade 4 toxicity:	Hold study treatment until resolution to \leq Grade 2. Resume at 1 dose level reduction unless the toxicity is a grade 4 electrolyte imbalance correctable within 48 hours or grade 4 vomiting that responds to maximum medical therapy within 48 hours. In such cases patients can resume treatment at the assigned dose without reduction at the Physician's discretion.
Hematologic toxicity RELATED to 8-chloro Adenosine	
Grade \geq 3 peripheral blood cytopenia not resolving to \leq Grade 2 by day 49 from start of cycle in patients who have less than 5% bone marrow blasts	No additional cycles of study drug will be administered
Other unspecified Non-Hematologic Toxicities considered UNRELATED to study agent	
Other unspecified events of any grade considered unlikely or not related to study agent.	Maintain treatment with study agent. Interruption of study treatment is permitted if the investigator consults with the Principal Investigator to determine that this is in the best interest of the participant.

*: See section 5.2 for additional criteria to resume, make up missed doses.

7.0 DATA AND SAFETY MONITORING PLAN

7.1 Definition of Risk Level

This is a Risk Level 4 study as defined in the [City of Hope Institutional Data and Safety Monitoring Plan](#) [policy dated 07/09/2014]. This determination was made because the study involves COH as IND holder and administering 8-chloro-adenosine as a single-dose agent.

7.2 Monitoring and Personnel Responsible for Monitoring

The Protocol Management Team (PMT) is responsible for monitoring the data and safety of this study. The PMT consists of the Principle Investigator (PI), Co-Investigator(s), Biostatistician, Research Protocol Nurse, and Clinical Research Coordinator. The PMT is required to submit periodic status reports (i.e., the PMT Report) according to the frequency prescribed in the [City of Hope Institutional Data and Safety Monitoring Plan](#) [policy dated 07/09/2014]. Important decisions made during PMT meetings (i.e., dose escalation, de-escalation, etc.) only need to be noted in the PMT Report submitted to the Data and Safety Monitoring Committee (DSMC).

Dose Escalation: This study will utilize the Phase I tracking log to monitor data and safety for dose escalation. The tracking log will contain dose levels administered, dose limiting toxicities (DLT), DLT-defining adverse events, and any details regarding dose escalation. The record of doses administered and resultant adverse events will be included in the PMT report. **Adverse Events and Serious Adverse Events**

The PI will be responsible for determining the event name, assessing the severity (i.e., grade), expectedness, and attribution of all adverse events.

Adverse Event (AE) - An adverse event is any untoward medical experience or change of an existing condition that occurs during or after treatment, whether or not it is considered to be related to the protocol intervention.

Reporting Non-serious Adverse Events – Adverse events will be collected after the patient is given the study treatment or any study related procedures. Adverse events will be monitored by the PMT. Adverse events that do not meet the criteria of serious OR are not unanticipated problems will be reported only in the PMT Report.

Serious Adverse Event (SAE) [Modified from the definition of unexpected adverse drug experience in [21 CFR 312.32](#)] - defined as *any expected or unexpected adverse events* that result in any of the following outcomes:

- Death
- Is life-threatening experience (places the subject at immediate risk of death from the event as it occurred)
- Unplanned hospitalization (equal to or greater than 24 hours) or prolongation of existing hospitalization
- A persistent or significant disability/incapacity
- A congenital anomaly/birth defect
- Secondary malignancy
- Any other adverse event that, based upon appropriate medical judgment, may jeopardize the subject's health and may require medical or surgical intervention to prevent one of the outcomes listed above (examples of such events include allergic bronchospasm requiring intensive treatment in the emergency room or at home, blood dyscrasias or convulsions that do not result in inpatient hospitalization, or the development of drug dependency or drug abuse).

Reporting Serious Adverse Events - begins after study treatment or any study related procedures. All SAEs occurring during this study, whether observed by the physician, nurse, or reported by the patient, will be reported according to the approved [City of Hope's Institutional policy](#) [policy effective date: 05/14/14]. Serious Adverse Events that require expedited reporting will be submitted electronically using [iRIS](#).

Adverse Event Name and Severity

The PI will determine the adverse event name and severity (grade) by using the CTCAE version 4.03.

Expected Adverse Event - Any event that does not meet the criteria for an unexpected event, OR is an expected natural progression of any underlying disease, disorder, condition, or predisposed risk factor of the research participant experiencing the adverse event.

Unexpected Adverse Event [[21 CFR 312.32 \(a\)](#)] – An adverse event is unexpected if it is not listed in the investigator's brochure and/or package insert; is not listed at the specificity or severity that has been observed; is not consistent with the risk information described in the protocol and/or consent; is not an expected natural progression of any underlying disease, disorder, condition, or predisposed risk factor of the research participant experiencing the adverse event.

Adverse Event Attribution

The following definitions will be used to determine the causality (attribution) of the event to the study agent or study procedure. **With Amendment v09:** A two level toxicity attribution scale will be used. In terms of attribution, all recorded adverse events will be classified as either related or unrelated to the study drug. Prior to this amendment a five level attribution scale (definite, possible, probable, unlikely, unrelated) was used.

Related -All adverse events will be considered relevant to determining dose-limiting toxicities and reporting unless the event can clearly be determined to be unrelated to the drug.

Unrelated -The AE is clearly not related to the investigational agent or study procedure and is attributable to another cause(s).

COH Held IND

Serious Adverse Events meeting the requirements for expedited reporting to the Food and Drug Administration (FDA), as defined in [21 CFR 312.32](#), will be reported as an IND safety report using the [MedWatch Form FDA 3500A for Mandatory Reporting](#).

The criteria that require reporting using the Medwatch 3500A are:

- Any unexpected fatal or life threatening adverse experience associated with use of the drug must be reported to the FDA no later than 7 calendar days after initial receipt of the information [[21 CFR 312.32\(c\)\(2\)](#)]
- Any adverse experience associated with use of the drug that is both serious and unexpected must be submitted no later than 15 calendar days after initial receipt of the information [[21 CFR 312.32\(c\)\(1\)](#)]
- Any follow-up information to a study report shall be reported as soon as the relevant information becomes available. [[21 CFR 312.32\(d\)\(3\)](#)]

The PI or designee will be responsible for contacting the Office of IND Development and Regulatory Affairs (OIDRA) at COH to ensure prompt reporting of safety reports to the FDA. OIDRA will assist the PI with the preparation of the report and submit the report to the FDA in accordance with the approved [City of Hope's Institutional policy](#) [policy effective date: 05/14/14].

Deviations and Unanticipated Problems

Deviation - A deviation is a divergence from a specific element of a protocol that occurred without prior IRB approval. Investigators may deviate from the protocol to eliminate immediate hazard(s) for the protection, safety, and well-being of the study subjects without prior IRB approval. For any such deviation, the PI will notify the COH DSMC and IRB within 5 calendar days of its occurrence via [iRIS](#) in accordance with the [Clinical Research Protocol Deviation policy](#) [policy effective date: 11/07/11].

Single Subject Exception (SSE)

An SSE is a planned deviation, meaning that it involves circumstances in which the specific procedures called for in a protocol are not in the best interests of a specific patient. It is a deviation that is anticipated and receives prior approval by the PI and the IRB. The SSE must be submitted as a "Single Subject Exception Amendment Request" via [iRIS](#) in accordance with IRB guidelines and the [Clinical Research Protocol Deviation policy](#) [policy effective date: 11/07/11]. An IRB approved SSE does not need to be submitted as a deviation to the DSMC.

Unanticipated Problem (UP) – Any incident, experience, or outcome that meets all three of the following criteria:

1. Unexpected (in terms of nature, severity, or frequency) given the following: a) the research procedures described in the protocol-related documents such as the IRB approved research protocol, informed consent document or Investigator Brochure (IB); and b) the characteristics of the subject population being studied; **AND**
2. Related or possibly related to participation in the research (possibly related means there is a reasonable possibility that the incident, experience, or outcomes may have been caused by the drugs, devices or procedures involved in the research); **AND**
3. Suggests that the research places subjects or others at greater risk of harm (including physical, psychological, economic, or social harm) than previously known or recognized.

Any UP that occurs during study conduct will be reported to the DSMC and IRB in accordance with the [City of Hope's Institutional policy](#) [policy effective date: 05/14/14] using [iRIS](#).

[figure not shown]
COH Held IND

The Office of IND Development and Regulatory Affairs (OIDRA) will assist the PI in reporting the event to the Food and Drug Administration (FDA).

